### **Study Site Visits (at study sites)**

Participants should adhere to the visit schedule and procedures in the [SoA](#).

If a participant discontinues or withdraws from the study prior to Week 312, the early discontinuation visit will follow the same procedures as the Week 312 visit (End of Study), per the SoA.

Every effort should be made to ensure that protocol-required tests and procedures are completed as described. However, it is anticipated that from time to time there may be circumstances outside the control of the investigator that may make it unfeasible to perform the test. In these cases, the investigator must take all steps necessary to ensure the safety and well-being of the participant. When a protocol-required test cannot be performed, the investigator will document the reason for the missed test and any corrective and preventive actions that he or she has taken to ensure that required processes are adhered to as soon as possible. The study team must be informed of these incidents in a timely manner.

In the event that any of the post-infusion procedures listed below cannot be performed according to the timepoints specified in the study protocol, due to COVID-19 restrictions or otherwise, it is recommended that they be performed at the next on-site visit or unplanned visit. Even though the procedures may have been performed at a subsequent visit, any procedures not performed according to the timepoints specified in the study protocol are still considered protocol deviations.

- ECG
- Liver ultrasound
- HJHS
- Global Hemostasis Markers

## **8.1. Efficacy Assessments**

### **8.1.1. Hemophilic Bleeding Episodes and Treatment**

An eDiary, a handheld device, will be provided to all participants on Visit 1. The participants are required to enter any occurrence of hemophilic bleeding episodes (including date, time, location, and etiology) and any exogenous FIX replacement (including date, time, reason, and dose) required to treat the bleeds in the eDiary (see [Appendix 7](#)). If bleeding episodes or treatments are not entered in the eDiary during the appropriate time window, data should be entered by the investigator (or appropriate site staff member) according to the process in place with appropriate source documentation in the participant's medical record. The bleeding episodes and exogenous FIX replacement data mentioned above will be referred to as "eDiary data" regardless of how it is collected (ie, via the handheld device or according to the process in place).

As part of the process in place, participants should communicate all bleeds and all relevant infusion data that was not entered into the eDiary within the appropriate time window (ie, "late eDiary entries") to the investigator (or appropriate site staff member). The site staff should counsel participants regarding late eDiary entries and emphasize the importance of being compliant with expected eDiary entries (eg, it helps monitor the participant's condition throughout the study). In the event of continued late eDiary entries or non-use of the eDiary device (ie, non-compliances), the site staff should remind the participant that he will be expected to report all bleeds and all relevant infusion data to the site staff on a contemporaneous basis and that he may be expected to surrender his eDiary. The site staff will be expected to enter the information, provided by the participant, into the CRFs with appropriate source documentation in the participant's medical record for the remainder of the study.

In the event that a participant may have to resume FIX prophylaxis treatment at some point after IP infusion, prophylaxis FIX infusion data will not have to be reported on the eDiary (or conveyed to the study site staff on contemporaneous basis) after Week 78 (Visit 14). However, bleeds and non-prophylactic infusions (eg, On-demand and Preventative) would continue to be reported for these participants throughout the course of the study. Prescribed FIX prophylaxis replacement therapy will continue to be captured (eg, particularly any change in regimen), by the site staff, using the "FIX Replacement (Prescribed Dose)" CRF.

During the site visits, the investigator (or qualified designee) will review eDiary data with the participants. Bleeding episodes and any exogenous FIX treatments will be reviewed to ensure consistency between the medical record and/or eDiary and the CRFs.

Bleeding episodes requiring treatment with FIX product will count toward the determination of bleeding episode frequency and the eDiary and/or medical record will serve as the source document for bleeding episodes.

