## 6.5. Concomitant Therapy

Any concomitant therapy such as procedures, medication, or vaccine use (including: prescription and nonprescription medications, including over-the-counter and alternative preparations such as herbal remedies, vitamins, and health food supplements) in the 30 days prior to screening and during screening must be recorded at Baseline on the participant's eCRF, according to instructions for eCRF completion. With the exception of FIX replacement therapy, concomitant therapy throughout the study must be recorded on the eCRF as follows:

- All concomitant therapy (including any COVID-19 vaccinations – see [Section 10.13.4](#)) during the Short-term Monitoring Period (up to and including 52 weeks post-infusion).
- The concomitant therapy associated with adverse events (AEs) reported during the Long-term Monitoring Period (Week 53 post-infusion to EOS). See [Section 8.3.1](#) for AE recording requirements.
- All surgical procedures, including elective surgeries, will be recorded throughout the study. Additional information regarding surgeries (eg, blood loss and/or transfusion amounts) will be collected on relevant CRF(s).

The records for concomitant therapy will include:

- Reason for use.
- Dates of administration including start and end dates.
- Dosage information including dose and frequency.

The sponsor's medical monitor should be contacted if there are any questions regarding concomitant or prior therapy.

Participants taking medication routinely for a pre-existing condition should be on a regimen, which has been stable for at least 3 weeks, and ideally dosage should not be changed during the first year after PF-06838435 infusion.

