### 6.5.1. Allowed Therapy

During the study participants are requested to suspend their FIX prophylaxis regimen after infusion of PF-06838435, but may take:

- FIX replacement therapy is allowed, as needed. The infusion data (specific product, date, time, dosage, reason) is to be recorded in the eDiary.
- For a bleeding event, the investigator / study staff will recommend the appropriate dose of FIX to treat the bleed because the dose of factor concentrate should include the recent steady-state PF-06838435 induced FIX activity levels to avoid overdosing resulting in a potential thrombotic event. The table in [Appendix 8](#) provides guidelines for target FIX levels based on bleed type.
- A participant may resume prophylaxis if the PF-06838435 treatment is not efficacious, defined for this study as:
  - FIX activity after 12 weeks of  $\leq 2\%$  (in the absence of a confirmed FIX inhibitor) as determined by the central laboratory on 2 consecutive samples collected within a 2 week period;and/or
  - Over a 4-week period (in the absence of a confirmed FIX inhibitor);
    - 2 or more spontaneous bleeds into a major joint and/or target joint;or
    - 3 or more spontaneous bleeds (consisting of joint bleeds and/or significant soft tissue/muscle or other site bleeds). Significant spontaneous bleeds are defined as those that lead to a transient or persistent loss of function.

The investigator is to discuss the case with the sponsor's medical monitor prior to resumption of prophylaxis. Dosing of prophylaxis will take into account the current steady-state FIX activity level. A participant who resumes prophylaxis may choose to discontinue it; however, prior to discontinuation, the investigator is to discuss with the sponsor's medical monitor.

Additional allowed therapies include the following:

- COX-2 inhibitors and topical NSAIDs, where medically necessary
- HIV therapy

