2.1.2.2. Annualized Infusion Rate (AIR)

The key secondary endpoint, AIR of exogenous FIX from Week 12 to Month 15 will be tested for superiority vs AIR with FIX prophylaxis replacement regimen during the Pre-Infusion Period.

- Population: Patients who are male adults with moderately severe to severe hemophilia B (FIX:C ≤2%) who have received infusion of PF-06838435.
- Variable: AIR of exogenous FIX pre-PF-06838435 infusion and from Week 12 to Month 15 post PF-06838435 infusion
- Intercurrent event(s): Resumption of FIX prophylaxis does not affect this analysis. This endpoint includes all infusions during the observation period regardless of purpose of FIX replacement therapy, i.e., includes infusions to treat bleeding, procedure related, for preventive purpose, or for prophylaxis regimen, etc.
- Population-level summary: Difference in mean AIR comparing AIR from Week 12 to Month 15 post PF-06838435 infusion to AIR during the Pre-Infusion Period.

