3.2.2. Annualized Infusion Rate (AIR)

Annualized infusion rate of exogenous FIX from Week 12 to Month 15 is considered as a key secondary endpoint. All infusions during the observation time period for any purpose including: to treat bleeding, or for preventive purpose, or perioperative, or if prophylaxis FIX regimen is resumed, will be included in the calculation of AIR. Similar endpoints will be calculated for the subsequent time periods, >Month 15 to Month 24; >Month 24 to Month 36; >Month 36 to Month 48; >Month 48 to Month 60; and >Month 60 to Month 72. AIR calculated for the above time period will be referred to as AIR Year 2, AIR Year 3, AIR Year 4, AIR Year 5, and AIR Year 6.

For participants with incomplete data for the analysis time period, or if a participant has not yet been followed for the entire analysis time period, all infusion data during that period will

be included in the analysis and summarized as such. AIR for each participant will be annualized as below:

AIR= (Number of infusions (for any reason) during the given time period x 365.25) (Date of last day – date of first day +1) in that time period)

Similarly, the baseline AIR data will be based on data collected in the Pre-Infusion Period while participants were on a prophylaxis FIX replacement regimen. For the baseline AIR calculation, all infusions will be included in the AIR calculation including those to treat bleeding (on-demand), for prophylaxis, for preventive purposes, or perioperative infusions. The AIR baseline will be annualized using the above formula.

The list of participants who resumed FIX prophylaxis and the date of resumption will be confirmed and provided to the programming team by the clinical team before database release. The percentage of the participants who resume a FIX prophylaxis regimen will be determined for the overall time period.

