3.2.4. Annualized FIX Consumption

Annualized FIX consumption will be reported by IU/kg and total units, and a similar approach of data collection and endpoint derivation as described for AIR will be used. This endpoint of FIX consumption not only measures the number of infusions but also the total units consumed.

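### Resumed-prophylaxis infusions need not be reported after Week 78, yet AIR and FIX consumption for Years 2 to 6 must count them, and the SAP has no rule for deriving them

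*Protocol*

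**What the plan says.** **Collection.** Protocol 6.5.1 makes the eDiary the record for FIX use: "The infusion data (specific product, date, time, dosage, reason) is to be recorded in the eDiary". The general concomitant-therapy record offers no second source, because Protocol 6.5 opens its rule with "With the exception of FIX replacement therapy, concomitant therapy throughout the study must be recorded on the eCRF as follows". Protocol 8.1.1 then lifts the duty for resumed prophylaxis after Week 78 (Visit 14): "prophylaxis FIX infusion data will not have to be reported on the eDiary", and it need not be passed to the site as it happens either. Bleeds, on-demand infusions and preventative infusions stay reportable. For prophylaxis, what remains is the regimen: "Prescribed FIX prophylaxis replacement therapy will continue to be captured (eg, particularly any change in regimen), by the site staff", on the CRF for prescribed FIX replacement doses.

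**Endpoint.** The AIR estimand in SAP 2.1.2.2 reads "This endpoint includes all infusions during the observation period regardless of purpose of FIX replacement therapy". SAP 3.2.2 lists resumption explicitly ("or if prophylaxis FIX regimen is resumed, will be included in the calculation of AIR") and carries the definition through to Month 72. Protocol 9.4.1 likewise describes late AIR as covering both on-demand and prophylaxis infusions. For FIX consumption, SAP 3.2.4 says "a similar approach of data collection and endpoint derivation as described for AIR will be used". SAP 6.2.2.2 tests AIR in Years 2 to 6 and over the whole follow-up for superiority, and reports the percentage of participants with no exogenous FIX infusion in each period.

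**Link between the two.** SAP 3.2.2 names no data source. SAP 3.1.1 matches bleeds to infusions using the Infusion eDiary or Infusion CRF, and the SAP version history mentions an eDiary CRF for deriving ABR and AIR. The prescribed-dose CRF appears nowhere in the SAP. SAP 5.3 rules out imputation unless Section 3 provides for it, and Section 3 provides none for AIR or consumption.

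**The concern.** The numerator and denominator of late AIR rest on different information. The formula in SAP 3.2.2 divides by every day in the period and removes no time after resumption, whereas ABR in SAP 3.1.1 drops both the events and the days. Once prophylaxis infusions go unreported, the days stay in and the infusions fall out.

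This matters because of the role given to AIR. Protocol 9.1.1 leaves post-resumption data out of the total-bleed ABR and points to AIR and FIX consumption as the endpoints through which resumption is assessed. After Week 78, treatment failure should therefore be visible in these two endpoints. Read literally, the plan would score a resumer close to zero and, if he had no on-demand or preventative infusion, count him as infusion-free in Years 3 to 6. The error can only favour gene therapy, and it falls on endpoints listed to show durability up to six years.

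**Working it through.** No figure in the plan depends on this rule, so there is none to reproduce first. The check is day arithmetic, then an illustration.

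**Day convention.** Week 12 less 2 days: 12 × 7 − 2 = Day 82. Week 65 plus 2 weeks: 65 × 7 + 14 = Day 469. Both match the SAP. On the same convention Week 78 is 78 × 7 = Day 546, which is 77 days after the primary window closes.

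**Share of each period in which resumed prophylaxis is not reportable**

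- Week 12 to Month 15 (Day 82 to 469): none.
- Year 2 for AIR (Day 470 to 730, SAP 5.2): 730 − 470 + 1 = 261 days, of which 730 − 546 = 184 are affected, 184/261 = 70.5%. Across the ±2-week window of Visit 14 (Day 532 to 560) the count is 198 to 170 days, 75.9% to 65.1%.
- Years 3 to 6: all days.
- Overall, taken as Day 82 to Day 2190 (6 × 365): 2190 − 82 + 1 = 2,109 days, of which 2190 − 546 = 1,644 are affected, 78.0%.

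**Effect on mean AIR.** Understatement = (m/40) × r × affected share, where m is the number of participants on resumed prophylaxis on every affected day and r is their yearly infusion rate. The documents give neither m nor r. Assumed rates: every 2 weeks, 365.25/14 = 26.09; weekly, 365.25/7 = 52.18; twice weekly, 365.25/3.5 = 104.36. I take m = 1 and m = 8; eight is the number SAP 6.2.2.2 uses as a threshold for summarizing time to resumption, not a forecast.

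| Period | m | Every 2 weeks | Weekly | Twice weekly |
|---|---|---|---|---|
| Year 2 | 1 | 0.46 | 0.92 | 1.84 |
| Year 2 | 8 | 3.68 | 7.36 | 14.71 |
| Each of Years 3 to 6 | 1 | 0.65 | 1.30 | 2.61 |
| Each of Years 3 to 6 | 8 | 5.22 | 10.44 | 20.87 |
| Overall | 1 | 0.51 | 1.02 | 2.03 |
| Overall | 8 | 4.07 | 8.13 | 16.27 |

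For one man on weekly prophylaxis throughout, true AIR is 52.2 per year; reported AIR would be 52.2 × 77/261 = 15.4 in Year 2 and 0 prophylaxis infusions afterwards. If only 60% of prescribed infusions were really given, the Years 3 to 6 figures shrink by 0.6, to 0.39–1.57 (m = 1) and 3.13–12.52 (m = 8). With m = 0 there is no effect. Unreported prophylaxis units cover the same share of days.

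**Percentage without infusions, Years 3 to 6.** Overstated by up to 1/40 = 2.5 points (m = 1) or 8/40 = 20 points (m = 8).

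**Would a late superiority test change?** Suppose all 40 had the same baseline regimen, k stay off prophylaxis (difference −r) and the rest truly return to it (difference 0). The paired t statistic has size √(39k/(40 − k)), so r cancels. On 39 degrees of freedom, two-sided: k = 3, t = 1.78, p = 0.083; k = 4, t = 2.08, p = 0.044; k = 5, t = 2.36, p = 0.023. A complete count would lose significance only if 37 or more of 40 had resumed.

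**The case against.** The best defence is that the information is not lost and that resumption will be visible. SAP 3.2.2 has the clinical team confirm the resumers and their dates before database release. SAP 6.2.2.2 reports the percentage resuming in every interval. Protocol 8.1.1 keeps the regimen on a CRF and has sites review FIX treatments with the participant. A resumer listed as infusion-free would contradict another planned table. This stands as mitigation, but none of it corrects the AIR, the units consumed or the infusion-free percentage, and reviewing recorded data does not restore infusions that nobody had to record.

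SAP 3.2.2 also says that participants with incomplete data are analysed on what is available. If unreported days were treated as incomplete and removed, the size of the error would differ. The SAP does not say that they are, and both the formula and the estimand keep them.

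The upper figures stack assumptions: eight resumers, a frequent regimen, and none stopping again, although Protocol 6.5.1 allows it ("A participant who resumes prophylaxis may choose to discontinue it"). In the Phase 1/2 experience in Protocol 2.2.2, 8 of 10 participants used no factor over 28 to 78 weeks. With no more than one resumer, the understatement in Years 3 to 6 is between 0 and 2.6 per year. That is a fair limit on the likely size, not an answer to the gap.

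**Conclusion.** The concern holds. The protocol waives collection of infusions that the endpoint definition requires, the infusion sources named in the SAP do not supply them, and its default is no imputation. Followed as written, the plan understates AIR and FIX consumption over about 70% of Year 2 and all of Years 3 to 6 for anyone on resumed prophylaxis, and can class such a participant as infusion-free.

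The reach is limited. The primary endpoint, the AIR test at the primary analysis and the rest of the gatekept sequence use data from before Week 78. Late superiority conclusions would rarely change. What is exposed is the size of the durability estimates at the final analysis, always in the favourable direction. The day shares follow from the documents, apart from the assumed span of the overall period; the AIR shifts depend on an unknown number of resumers and unknown regimens, and vanish if nobody resumes. The point should be fixed before the final analysis.

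**What to change.** Add one rule to SAP 3.2.2, 3.2.4, 6.2.2.2 and 6.2.4:

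- For days after Week 78 on resumed prophylaxis, derive infusions and international units from the prescribed-dose CRF and add the reported on-demand and preventative infusions.
- Run the derivation from the regimen start date to any stop date on that CRF. Do not start it at the investigator's decision date, which SAP 3.1.1 uses for ABR.
- Classify the participant as not infusion-free in every interval containing such days.
- Label these counts as prescribed rather than administered, and note that the baseline counts are reported infusions.
- Add a sensitivity analysis over adherence. Protocol Section 2 cites a study in which 43% of patients adhered to prophylaxis; that is a share of patients, not of doses, so it supports varying adherence without fixing the values. Levels such as 60%, 80% and 100% are examples for the sponsor to replace and justify.

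The cost is SAP text and programming, with no new burden on participants. The form itself is not in the documents, so the sponsor must confirm that it holds frequency, dose and complete start and stop dates. The price is prescribed rather than actual use for a few participants, and somewhat less favourable late figures.

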### **8.1.2. Joint Assessments**

See [Appendix 7](#) for definition of target joints. Investigator will assess the health of the target joint(s), identified at screening, as per the [SoA](#). A target joint is considered resolved when there are  $\leq 2$  bleeds into the joint within a 12-month period.

#### **8.1.2.1. Hemophilia Joint Health Score (HJHS)**

Swelling, on motion Joint assessments will be performed using the Hemophilia Joint Health Score (HJHS) version 2.1 ([Appendix 12](#)) to evaluate joint total (swelling, duration of swelling, muscle atrophy, crepitus on motion, flexion loss, extension loss, joint pain, and strength) and global gait scores. The HJHS is designed for use by physiotherapists. In order to maintain precision and validity of the tool (score), the developers strongly recommend that the tool be used by physiotherapists/healthcare professionals who have hemophilia-related expertise/experience and have been trained in the use of clinical measures, musculoskeletal assessments and specifically administration of the HJHS. Training on use of the HJHS assessment tools will be provided, by the sponsor, and must be completed by the investigator or designee(s) performing these assessments.

Study participants with prosthetic joints should still have the joints evaluated. The replaced joint should be scored on all items that are possible. Any item that is not tested, for whatever reason, will need to be scored as NE (non-evaluable). This might pertain particularly to the gait skills of running and hopping on 1 leg if the participant is unable to perform the skill or the assessor perceives risk (eg, of bleeding or injury) to the participant if he does perform these skills.

#### **8.1.2.2. Magnetic Resonance Imaging (MRI) to Evaluate Joints**

Some participants (n~20), who consent to participate in an optional sub-study, will undergo MRI exams to assess damage within joints by evaluating soft-tissue changes and osteochondral changes. These participants will be chosen based on the availability of MRI at the site and participant willingness to undergo the procedure. The MRI scanning protocol will include acquisition of knees, elbows, and ankles. MRI scans will be acquired according to the [SoA](#). If the MRI can't be performed during the baseline period, it is acceptable to postpone this testing no later than Week 4/ Visit 6. If the baseline MRI as part of a sub-study could not be performed before or at Week 4/ Visit 6, the study participant does not need to do the 3 (Visit 17) and 6 (Visit 20) year follow-up MRIs. All details of the MRI acquisition will be captured in a separate scanning guide. At a minimum, joint images will be reviewed following the extended MRI scale with a final score combining soft-tissue and osteochondral sub-scores. All details of the independent review will be captured in a separate Imaging Charter.

##### **8.1.2.2.1. Management of Incidental Findings**

An incidental finding is one unknown to the participant that has potential health or reproductive importance, which is discovered unexpectedly in the course of a research study, but is unrelated to the purpose and beyond the aims of the study.

MRI images will be reviewed by a central review facility. The purpose of this review is to evaluate images for soft tissue and osteochondral changes. Central image review is not a complete medical review of the participant. If during the central review process, an unexpected observation is identified and this finding could, in the opinion of the central reviewer, have a significant health or reproductive consequence, this finding may be shared with the study sponsor for disclosure to the principal investigator. All follow-up testing and final diagnosis will be left to the discretion of the medical professionals at the site or those with an existing physician-participant relationship. The principal investigator will be responsible for reporting any adverse events identified from incidental findings as described in the Adverse Event Reporting section. Identification of such incidental findings during the central review process should not be expected, and the site maintains responsibility for performing a general safety review of all images as per site protocols.

MRI images will not be evaluated using a real-time reading paradigm and therefore there may be a significant delay between image submission and realization of an incidental finding.

